#### 4.1.2.3 NCPD

For calculation of NCPD, see section 3.4.2.

#### 4.1.2.4 **PROPORTION OF PARTICIPANTS WITH FLARE AFTER CRMIN**

For participants who achieve CRmin (in 1904 or 1905), the proportion of participants who experience a flare in 1905 after CRmin (as assessed by the investigator) will be derived within the roll-over phase (flare after CRmin in 1904), within each treatment period (flare after CRmin within the treatment period), within the follow-up phase (flare after CRmin prior to follow-up phase) and over the entire study (ie, whether the participant achieves the status during the roll-over phase, during at least one treatment period or during the follow-up phase).

For the follow-up phase, participants who start the follow-up phase not on CRmin or CRoff will be excluded from this calculation.

Proportions will be calculated overall and by subgroup of disease status at roll-over.

SGS	Statistical Analysis Plan	
ARGX-113-1905	Final analysis	Final 1.0 of 26APR2024

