#### **1.2** STUDY DESIGN

Document template OTH.STAT.010 v3

This is a prospective, multicenter, open-label extension (OLE) study on the efficacy, safety, participant outcome measures, tolerability, immunogenicity, PK, and PD of EFG PH20 SC in adult PV or PF participants, who participated in the antecedent study ARGX-113-1904 (1904).

Participants at the End of Study (EoS) visit or Early Discontinuation (ED) visit in 1904 will be given the option to enroll into 1905 after confirmation of eligibility while retaining the blinding of 1904. For each participant, the date of the baseline visit in 1905 will be the same as the date of the EoS/ED visit in 1904.

At baseline, participants will be treated according to their clinical status at EoS of 1904, as follows:

SGS	Statistical Analysis Plan	
ARGX-113-1905	Final analysis	Final 1.0 of 26APR2024

- Participants who have achieved CRmin or CRoff and are not currently in flare will be observed every 4 weeks through on-site visits without EFG PH20 SC treatment. In participants who have achieved CRmin (oral prednisone ≤10 mg per day for 2 months [8 weeks]), prednisone tapering may be pursued upon investigator's judgment until participants achieve CRoff.
- Participants in CR who have not achieved CRmin will receive weekly EFG PH20 SC administrations of 1000 mg while continuing the add-on therapy of oral prednisone until CRmin is achieved. Prednisone tapering may be pursued upon investigator's judgment until participants achieve CRoff. Participants will be treated through on-site visits or through home visits with an on-site visit once every 4 weeks.
- Participants who have achieved DC but not CR will receive weekly onsite administrations of 1000 mg EFG PH20 SC with an add-on therapy of oral prednisone until CR has been achieved, and then will continue to receive weekly EFG PH20 SC administrations of 1000 mg until CRmin is achieved either on-site or through home visits with an on-site visit once every 4 weeks.
- Participants under certain conditions of treatment failure as defined below, or participants with flare after having achieved CRmin, may roll over prematurely into 1905 and will be treated with EFG PH20 SC at a dose of the second s

The following types of treatment failure are considered here:

- absence of DC with oral prednisone 1.5 mg/kg/day for a minimum of 3 weeks
- participants who roll over due to prednisone-related SAE who have not achieved DC, or

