#### 4.1.2.6 OTHER EFFICACY ENDPOINTS

Other efficacy endpoints are:

1. Number of flares: count number of flares as assessed by the investigator. A new flare only emerges after a new DC. Number of flares are counted over:

- the entire study (the whole roll-over, treatment + follow-up phase)
- within each treatment period
- within each treatment period between first DC and CRmin (or end of treatment period for participants without CRmin).
- within each treatment period after CRmin.

For participants who enter the study because of a flare in the 1904 study, the initial flare (at the roll-over visit) will not be counted. Flare counts will be presented overall and by subgroup of disease status at roll-over.

2. Proportion of treatment failures as assessed by the investigator over the treatment phase. Specific reasons for treatment failure can be derived as follows in following order:

- absence of DC: if participant did not achieve DC as assessed by the investigator
- flare: if previous reason is not applicable, the reason must be a flare between DC and CRmin that is not controlled by a prednisone dose that is 2 dose levels above the dose at which the flare is observed and that is a least 0.3mg/kg qd

3. PDAI at each visit: PDAI activity subscores (mucosal, skin and scalp), PDAI activity score and PDAI total score are assessed by the investigator at each visit.

4. QoL at each visit: ABQOL (17 items) and EQ-5D-5L (i.e., mobility, self-care, usual activities, pain/discomfort, anxiety/depression and VAS) are assessed by the investigator at baseline, start of re-treatment, CRmin and Week 52/EoT/ET. A total ABQOL score is calculated as the sum of all 17 items score 0 to 3 with higher score indicating worse condition. Missing items are imputed with the average score of the present items if at least half (9) of the items are present. The total score is rounded to the highest integer.

5. C-GTI at each visit: Composite Glucocorticoid Toxicity Index comprises the Aggregate Improvement Score (AIS) and the Cumulative Worsening Score (CWS) (health impact of GC) and is measured at baseline, Week 26 and Week 52/EoT/ET. AIS and CWS are calculated for the first 26 week period (W26), for the last 26 week

SGS	Statistical Analysis Plan	
ARGX-113-1905	Final analysis	Final 1.0 of 26APR2024

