#### 4.1.3.4 **PROPORTION OF PARTICIPANTS WITH FLARE AFTER CRMIN**

Frequency tabulations will be provided of the percentage (with 95% exact confidence interval) of PV participants and all participants (PV+ PF) experiencing a flare after CRmin within the roll-over phase, within each treatment period, within the follow-up phase and over the entire study. The table will be repeated by disease status at roll-over. The denominator of these tables is restricted to participants who achieved CRmin in the applicable treatment period.

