#### Statistical Analysis Plan

Final analysis

Final 1.0 of 26APR2024

	Disease status at roll-over						
Endpoint	CRmin	CR	DC - no CR	Treatment failure	Flare after CRmin	Overall	
Period2,, n	Х	Х	Х	Х	Х	Х	
Follow-up	Х	Х	Х	Х	Х	Х	
Time to CR c							
Period 1			Х	Х	Х	Х	
Period2,, n	Х	Х	Х	Х	Х	Х	
Follow-up	Х	Х	Х	Х	Х	Х	
Time to CRmin c							
Period 1		Х	Х	Х	Х	Х	
Period2,, n	Х	Х	X	Х	Х	Х	
Follow-up	Х	Х	Х	Х	Х	Х	
Time to CRoff c							
Roll-over phase	Х						
Period 1		Х	Х	Х	Х	Х	
Period 2,, n	Х	Х	Х	Х	Х	Х	
Follow-up	Х	Х	Х	Х	Х	Х	
NCPD°	Х	Х	Х	Х	Х	Х	
Proportion flare after CRmin c							
Overall d	Х	Х	Х	Х	Х	Х	
Roll-over phase	Х						
Period 1		Х	Х	Х	Х	Х	
Period 2,, n	Х	Х	Х	Х	Х	Х	
Follow-up	Х	Х	Х	Х	Х	Х	
Time to flare after CRmin c							
Roll-over phase	Х						
Period 1		Х	Х	Х	Х	Х	
Period 2,, n	Х	Х	Х	Х	Х	Х	
Follow-up	Х	Х	Х	Х	Х	Х	
Number of flares c	Х	Х	Х	Х	Х	Х	
Proportion treatment failure c	Х	Х	Х	Х	Х	Х	
PDAI c						Х	
QoL, C-GTI						Х	

CONFIDENTIAL AND PROPRIETARY

System Version: 1.0, Status: Approved, Document ID: VV-TMF-172580

SGS	Statistical Analysis Plan	
ARGX-113-1905	Final analysis	Final 1.0 of 26APR2024
	Disease status at roll-ove	er

		Disease status at roll-over					
Endpoint	CRmin	CR	DC - no CR	Treatment failure	Flare after CRmin	Overall	
c Analysis done for a	c Analysis done for all participants (PV+PF) as well as for PV participants						
d Overall = during the	ing the roll-over phase (if applicable), during any treatment period or during the						
follow-up phase							

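### SAP 4.1.2.4 and 4.1.3.4 give conflicting denominators for the proportion with flare after CRmin, and neither gives the overall row an at-risk set

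*SAP*

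**What the plan says.** SAP 4.1.2.4 defines the population broadly: "For participants who achieve CRmin (in 1904 or 1905), the proportion of participants who experience a flare in 1905 after CRmin". It then splits the event by phase: "within the roll-over phase (flare after CRmin in 1904), within each treatment period (flare after CRmin within the treatment period". The follow-up event is a flare after a CRmin reached before follow-up began. The entire-study row asks "whether the participant achieves the status during the roll-over phase, during at least one treatment period or during the follow-up phase". The only at-risk exclusion in the section concerns follow-up: "For the follow-up phase, participants who start the follow-up phase not on CRmin or CRoff will be excluded from this calculation".

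SAP 4.1.3.4 presents these percentages with exact 95% confidence intervals for the roll-over phase, each treatment period, follow-up and the entire study, and adds: "The denominator of these tables is restricted to participants who achieved CRmin in the applicable treatment period".

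Flare after a 1904 CRmin is a recognised way into this study. SAP 1.2 says that "participants with flare after having achieved CRmin, may roll over prematurely into 1905", and SAP 2.5 makes it one of the five disease-status categories at roll-over. In the overview table (SAP 4.1.3.7), the block labelled "Proportion flare after CRmin" marks the overall row for all five statuses and the roll-over row for the CRmin status only.

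**The concern.** The two sections describe the same tables with different denominators. One admits anyone with CRmin in either study. The other admits only those who reach CRmin inside a 1905 treatment period. Neither is the set of people who could have a post-CRmin flare in 1905.

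Rate of flare and time to flare are protocol secondary endpoints, and Tables 14.2.1.4.1 and 14.2.1.4.2 are listed as topline outputs. The percentage and its exact interval both depend on the denominator. Left as written, the programmer has to choose between the rules in an open-label study whose data already exist.

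**Working it through.** The plan states no expected flare rate, event count or power for this endpoint, so there is no figure to reproduce. SAP 1.3 gives a ceiling of about 213 participants and no numbers by entry status. The check is therefore one of logic, followed by an illustration on assumed counts.

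**1. Row by row**

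| Row | Event under 4.1.2.4 | Who can have it | 4.1.3.4 taken literally |
|---|---|---|---|
| Roll-over phase | flare following a 1904 CRmin | entered on CRmin/CRoff, not in flare | empty: CRmin was in 1904, and this phase is not a treatment period |
| Treatment period n | flare after CRmin reached in period n | reached CRmin in period n | fits |
| Follow-up | flare after a CRmin that predates follow-up | on CRmin/CRoff when follow-up starts | drops anyone on CRmin since 1904 and never treated in 1905 |
| Entire study | any of the above | at risk in at least one row | no single period applies |

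**2. Entrants already in flare, under 4.1.2.4**

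They meet the population condition through their 1904 CRmin. The overview table gives them no roll-over row. A treatment-period event needs CRmin in that period, and a follow-up event needs CRmin or CRoff when follow-up starts. An entrant who never regains CRmin can have no event in any row, yet remains in the overall denominator as flare-free.

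**3. Size under 4.1.2.4**

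Let A = participants at risk in 1905, x = those with an event, and F = flare entrants who never regain CRmin. The reported overall rate is x/(A+F) = (x/A) × A/(A+F). With A = 80 (assumed):

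| F | A/(A+F) | x = 20 (25.0% at risk) | x = 36 (45.0% at risk) |
|---|---|---|---|
| 5 | 80/85 = 0.941 | 20/85 = 23.5% | 36/85 = 42.4% |
| 10 | 80/90 = 0.889 | 20/90 = 22.2% | 36/90 = 40.0% |
| 20 | 80/100 = 0.800 | 20/100 = 20.0% | 36/100 = 36.0% |

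The Clopper-Pearson 95% interval for 20/80 is 16.0% to 35.9%; for 20/100 it is 12.7% to 29.2%.

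The effect is largest in the overall row of the 'Flare after CRmin' subgroup. With 20 entrants, 8 of whom regain CRmin and 3 of those flare (assumed), the row reads 3/20 = 15.0%, against 3/8 = 37.5% among those at risk.

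**4. Forcing 4.1.3.4 onto the overall row as 'any treatment period'**

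Split the same A = 80 as follows (assumed). Fifty enter on CRmin; 12 of them flare in the roll-over phase and are re-treated, and 5 of the 12 regain CRmin. Thirty first reach CRmin in 1905, and 8 of them flare. The at-risk rate is (12 + 8)/80 = 25.0%. The restricted denominator is 30 + 5 = 35. It drops the 50 − 12 = 38 who were never treated. It also drops 12 − 5 = 7 people whose roll-over flare 4.1.2.4 counts as an event. Events among the 35 give (5 + 8)/35 = 37.1%. So this reading removes the flare entrants who do not regain CRmin, but on these counts it moves the rate the other way.

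**The case against.** The best defence is that 'treatment period' in 4.1.3.4 is loose shorthand. SAP 2.4.1 sets event-type denominators by phase, period or subperiod as applicable, and 4.1.2.5 explicitly extends its censoring rule to the roll-over and follow-up phases. This is fair as to intent. It does not repair the sentence: CRmin would still have to be reached within the phase, whereas in the roll-over and follow-up rows it comes before the phase. The overall row would still have no rule.

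It is also true that results are repeated by disease status at roll-over, so the CRmin column is not diluted, and that Kaplan-Meier time to flare is reported separately. Both limit the harm to the overall row for all participants and the overall row of the 'Flare after CRmin' subgroup.

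A reader might infer a second bias: that a flare between disease control and CRmin in 1905 counts as an event because CRmin was once achieved in 1904, which would inflate the rate. The text does not support this. Within a treatment period, 4.1.2.4 counts only a flare after CRmin in that same period. A 1904 CRmin supports an event in the roll-over row, or in follow-up for someone on CRmin or CRoff when it starts. SAP 4.1.2.6 also counts flares before and after CRmin separately.

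**Conclusion.** The point stands as a conflict between two stated rules, not as a proven bias of known size. Under 4.1.2.4 and the overview table, the overall rate is the at-risk rate times A/(A+F). On the assumed counts with a 25% at-risk rate, the loss is 1.5 to 5.0 percentage points for F = 5 to 20. Only flare entrants who never regain CRmin cause this; those who regain it are properly at risk. Under 4.1.3.4 the roll-over row has no literal denominator, and people who are at risk leave the follow-up and overall rows.

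The omission does not look deliberate. SAP 4.1.2.1 removes people who already hold the status, and 4.1.2.2 computes a time to status only where the status can still be reached.

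A reader might also infer that the trial's main conclusion or an error rate is at risk. It is not: the primary objective is safety, there is no hypothesis test, and all efficacy endpoints are descriptive. The real effect depends on subgroup counts that the documents do not give.

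**What to change.** Replace the denominator sentence in 4.1.3.4 and align 4.1.2.4 with one denominator per row:

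- Roll-over phase: participants who entered on CRmin or CRoff, not in flare, and who have a roll-over phase.
- Treatment period n: participants who reach CRmin within period n.
- Follow-up: participants on CRmin or CRoff when follow-up starts (unchanged). This should not be widened to people who first reach CRmin during follow-up, whom 4.1.2.4 already excludes.
- Overall: participants at risk in at least one of these rows.

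Carry across from 4.1.2.6 the rule that "the initial flare (at the roll-over visit) will not be counted". It is written there for the number of flares only, and 4.1.2.4 has no matching sentence.

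Reconcile one related item, because the period rows depend on it. Table 1 in SAP 2.2.1 limits treatment period 1 to participants without CRmin or CRoff in 1904, while the overview table gives 'Flare after CRmin' entrants a Period 1 row.

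The cost is a few sentences of SAP text and the matching table footnotes, with no new data. The overall percentage may come out less favourable than under 4.1.2.4 as written.

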#### 4.1.2.5 TIME TO FLARE AFTER CRMIN

For participants who achieve CRmin (in 1904 or 1905) in a treatment period or in the follow-up phase, time to flare after CRmin will be calculated as:

(visit date of flare) - (date of CRmin) + 1.

Participants who do not experience a flare are censored at the end of the treatment period (or roll-over or follow-up phase as applicable).

For the roll-over phase of participants who enter study 1905 on CRmin, use date of roll-over visit instead of date of CRmin.

#### 4.1.2.6 OTHER EFFICACY ENDPOINTS

Other efficacy endpoints are:

1. Number of flares: count number of flares as assessed by the investigator. A new flare only emerges after a new DC. Number of flares are counted over:

- the entire study (the whole roll-over, treatment + follow-up phase)
- within each treatment period
- within each treatment period between first DC and CRmin (or end of treatment period for participants without CRmin).
- within each treatment period after CRmin.

For participants who enter the study because of a flare in the 1904 study, the initial flare (at the roll-over visit) will not be counted. Flare counts will be presented overall and by subgroup of disease status at roll-over.

2. Proportion of treatment failures as assessed by the investigator over the treatment phase. Specific reasons for treatment failure can be derived as follows in following order:

- absence of DC: if participant did not achieve DC as assessed by the investigator
- flare: if previous reason is not applicable, the reason must be a flare between DC and CRmin that is not controlled by a prednisone dose that is 2 dose levels above the dose at which the flare is observed and that is a least 0.3mg/kg qd

3. PDAI at each visit: PDAI activity subscores (mucosal, skin and scalp), PDAI activity score and PDAI total score are assessed by the investigator at each visit.

4. QoL at each visit: ABQOL (17 items) and EQ-5D-5L (i.e., mobility, self-care, usual activities, pain/discomfort, anxiety/depression and VAS) are assessed by the investigator at baseline, start of re-treatment, CRmin and Week 52/EoT/ET. A total ABQOL score is calculated as the sum of all 17 items score 0 to 3 with higher score indicating worse condition. Missing items are imputed with the average score of the present items if at least half (9) of the items are present. The total score is rounded to the highest integer.

5. C-GTI at each visit: Composite Glucocorticoid Toxicity Index comprises the Aggregate Improvement Score (AIS) and the Cumulative Worsening Score (CWS) (health impact of GC) and is measured at baseline, Week 26 and Week 52/EoT/ET. AIS and CWS are calculated for the first 26 week period (W26), for the last 26 week

SGS	Statistical Analysis Plan	
ARGX-113-1905	Final analysis	Final 1.0 of 26APR2024

period (W52) and overall (Endpoint). The last post-baseline assessment (Endpoint) is considered as the overall CWS/AIS and is calculated as a cumulative score over all post-baseline timepoints. Details on calculation of CWS/AIS are provided in appendix 9.1. The complementary GTI specific list (GTI-SL) will only be listed.

### 4.1.3 Presentation of results

#### 4.1.3.1 **PROPORTION OF PARTICIPANTS WHO ACHIEVE CRMIN AND CROFF**

Frequency tabulations will be provided of the percentage (with 95% exact confidence interval) of PV participants and all participants (PV+ PF) achieving CRmin within each treatment period, within the follow-up phase and over the entire study. The table will be repeated by disease status at roll-over.

Similar tables will be provided for the percentage of participants achieving CRoff.

#### 4.1.3.2 TIME TO DC, CR, CRMIN AND CROFF

Time to DC, Time to CR, Time to CRmin and Time to CRoff will be descriptively presented with median times, quantiles and number and percentage of participants censored and with event, as obtained through Kaplan-Meier analysis.

The tables will be produced for PV participants and for all participants (PV+PF), also overall and by disease status at roll-over.

#### 4.1.3.3 CUMULATIVE PREDNISONE DOSE AND NCPD

Cumulative prednisone dose and NCPD will be summarized using descriptive statistics as descripted in section 3.4.3.

Tables will be provided for PV participants and all participants (PV+PF), overall and by disease status at roll-over.

#### 4.1.3.4 **PROPORTION OF PARTICIPANTS WITH FLARE AFTER CRMIN**

Frequency tabulations will be provided of the percentage (with 95% exact confidence interval) of PV participants and all participants (PV+ PF) experiencing a flare after CRmin within the roll-over phase, within each treatment period, within the follow-up phase and over the entire study. The table will be repeated by disease status at roll-over. The denominator of these tables is restricted to participants who achieved CRmin in the applicable treatment period.

#### 4.1.3.5 TIME TO FLARE AFTER CRMIN

Time to flare after CRmin will be descriptively presented with median times, quantiles and number and percentage of participants censored and with event, as obtained through Kaplan-Meier analysis.

The tables will be produced for PV participants and for all participants (PV+PF) who achieved CRmin, also overall and by disease status at roll-over.

#### 4.1.3.6 OTHER EFFICACY ENDPOINTS

Descriptive statistics will be provided for the number of flares. Tables will be provided for PV participants and all participants (PV+PF), overall and by disease status at roll-over.

SGS	Statistical Analysis Plan	
ARGX-113-1905	Final analysis	Final 1.0 of 26APR2024

Frequency tabulations will be provided for the percentages of treatment failure (with 95% exact confidence interval) and its different reasons, overall and by disease status at roll-over.

PDAI activity subscores (mucosal, skin and scalp), PDAI activity score and PDAI total score will be summarized by means of descriptive statistics at each analysis visit. Actual values, changes from baseline and percent changes from baseline will be tabulated by analysis visits overall. Additionally, changes and percent changes versus 1904 baseline will be tabulated by analysis visits overall. Furthermore, actual values, changes from TPnB and percent changes from TPnB will be tabulated by analysis visits by period/subperiod. Tables to be provided for PV participants and for all participants (PV+PF).

Frequency tabulations will be provided for the percentages of participants within each outcome of QoL questionnaire items (ABQOL and EQ-5D-5L) at each analysis visit. Additionally, cumulative percentages (starting with the best outcome result) will be calculated. Descriptive statistics will be provided for the total ABQOL score and for the EQ-5D-5L VAS score.

Descriptive statistics will be provided for the C-GTI scores AIS and CWS. C-GTI will be analysed on complete cases: i.e. participants with C-GTI at baseline and at least one post-baseline visit. Participants where first post-baseline GTI improvements/worsening have not been obtained with respect to the baseline moment but with respect to a later moment (i.e. no GTI assessment at baseline visit) are excluded from analyses and are only listed.

#### 4.1.3.7 **OVERVIEW OF ANALYSES FOR EFFICACY ENDPOINTS**

Following table summarizes the analyses to be done for efficacy using Roll-over set:

	Disease status at roll-over					
Endpoint	CRmin	CR	DC - no CR	Treatment failure	Flare after CRmin	Overall
Proportion CRmin c						
Overall d	X a	Х	Х	Х	Х	Х
Period 1		Х	Х	Х	Х	Х
Period 2,, n	Х	Х	Х	Х	Х	Х
Follow-up	Х	Х	Х	Х	Х	Х
Proportion CRoff c						
Overall d	X b	Х	Х	Х	Х	Х
Roll-over phase	X b					
Period 1		Х	Х	Х	Х	Х
Period 2,, n	Х	Х	Х	Х	Х	Х
Follow-up	Х	Х	X	Х	Х	Х
Time to DC c						
Period 1				Х	Х	Х

Document template OTH.STAT.010 v3

Page 40 of 84

CONFIDENTIAL AND PROPRIETARY

System Version: 1.0, Status: Approved, Document ID: VV-TMF-172580

